#### 15. BLINDING/UNBLINDING

This is a multicenter, randomized, double-blind, vehicle-controlled, parallel group comparison study of HBP Foam and VEH Foam. Blinding is important for the integrity of this clinical drug trial and all personnel involved with the clinical assessments of subjects must remain blinded with respect to the identity of the test articles dispensed to the subjects.

However, the blind may be broken in the event of a medical emergency in a subject, in which knowledge of the test article identity is critical to the subject's management. Before breaking the blind for a subject, the investigator should determine that the information is necessary (i.e., that it will alter the subject's immediate management). In many cases, particularly when the emergency is clearly not test article related, the problem may be effectively managed by assuming that the subject is receiving active product without the

need for unblinding. The need to break the blind should first be discussed with the responsible Medical Monitor and the best method to do this will be determined.

#### 16. CLINICAL SUPPLIES

#### 16.1 Test Article Information

Test articles will be packaged and labeled by the Sponsor or designee. The identities of the products will be blinded prior to receipt by the sites. Detailed information on the packaging/labeling, blinding/unblinding, storage and preparation, dispensing, and accountability are included in Appendix 4.

# 16.2 Supplies Provided by Therapeutics, Inc.

- CRFs
- Site regulatory binder
- Bland emollient
- UPT kits
- Weighing scales for test articles (if necessary)

# 16.3 Supplies Provided by Investigator

- Urine collection containers
- Personal computer to store and view study photographs (designated study sites only)

#### 17. STATISTICAL CONSIDERATIONS

#### 17.1 Sample Size

A sample size of 200 subjects for each treatment group (i.e., HBP Foam and VEH Foam) is estimated to be sufficient to detect a true treatment difference of "success" rates based on Fisher's Exact Test with a power of 0.85 and a Type I error rate of 0.05 (two-tailed).

Approximately 400 subjects are expected to be consented and enrolled into this study and assigned in a 1:1 randomization to one of two treatments: HBP Foam (200) and VEH Foam (200).

## 17.2 Endpoints

#### 17.2.1 Efficacy Endpoints

IGA scores and the clinical signs of psoriasis will be dichotomized to "treatment success" or "treatment failure" where "treatment success" is defined as a score of 0 or 1 representing "cleared" or "almost cleared" with at least a two grade decrease in severity score relative to Baseline.

The primary efficacy endpoint will be the proportion of subjects with IGA "treatment success" at Day 15.

The key secondary efficacy endpoints are:

- The proportion of subjects rated a "treatment success" for plaque elevation at Day 15.
- The proportion of subjects rated a "treatment success" for scaling at Day 15.
- The proportion of subjects rated a "treatment success" for erythema at Day 15.

#### Other efficacy endpoints include:

- The proportion of subjects with IGA "treatment success" at Day 8.
- The proportion of subjects rated a "treatment success" for each of the clinical signs of psoriasis (scaling, erythema, and plaque elevation) at Day 8.
- Change from Baseline in pruritus score at Day 15.
- Changes in percent BSA with active psoriasis in the Treatment Area at Days 8 and 15.

#### 17.2.2 Safety Endpoints

Safety endpoints will include assessment of LSRs associated with topical application of corticosteroids (telangiectasia, skin atrophy, burning/stinging, folliculitis, and edema), AEs, and SAEs.

#### 17.3 Statistical Methods

All statistical processing will be performed using SAS® unless otherwise stated. Statistical significance for the primary efficacy endpoint will be based on a two-tailed test of the null hypothesis at the alpha=0.05 level of significance.

Efficacy analyses will be performed primarily for the intent-to-treat (ITT) population. Efficacy analyses using the per-protocol (PP) population will be in support of the ITT analyses.

The Safety population will include all subjects enrolled in the study who were dispensed and applied test article at least once. Subjects will apply their first application of test article in the clinic during their Baseline Visit on Day 1. Subjects enrolled in the study who were

randomized and dispensed the test article will be considered the ITT population. Subjects will be included in the PP efficacy analyses if they have completed the study without significant protocol deviations. Subjects who discontinue from the study prematurely due to treatment failure, as determined by the investigator, will also be included in the PP population as treatment failures.

Demographic and baseline characteristics will be summarized by treatment group for the ITT, PP, and Safety populations. Frequency counts and percentages will be reported for categorical data and the number of subjects with non-missing data (n), mean, median, SD, minimum and maximum will be reported for the continuous variables.

### 17.3.1 Efficacy Analyses

## 17.3.1.1 Primary Efficacy Analysis

Efficacy will be demonstrated if the proportion of HBP Foam treated-subjects with IGA "treatment success" at Day 15 is statistically significantly greater than the proportion of VEH Foam-treated subjects that are "treatment successes" at Day 15 based on a two-sided test at the alpha=0.05 level of significance. The treatment groups will be compared with respect to IGA treatment success rates at Day 15 using the CMH test stratified by center.

Subjects without data at Day 15 will be considered to be treatment failures (i.e., to not have achieved the primary endpoint). Note: this definition includes subjects who drop out of the study prior to Day 15 for any reason.

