#### Safety Endpoint(s):

	Safety endpoints will include assessment of LSRs associated with topical application of corticosteroids (telangiectasia, skin atrophy, burning/stinging, folliculitis, and edema), AEs, and serious adverse events (SAEs).
Sample Size Calculations	A sample size of 200 subjects for each treatment group (i.e., HBP Foam and VEH Foam) is estimated to be sufficient to detect a true treatment difference of "success" rates (20% for HBP Foam versus 9% for VEH Foam) based on Fisher's Exact Test with a power of 0.85 and a Type I error rate of 0.05 (two-tailed).
	Approximately 400 subjects are expected to be consented and enrolled into this study and assigned in a 1:1 randomization to one of two treatments: HBP Foam (200) and VEH Foam (200).
Statistical Methods	All statistical processing will be performed using SAS® unless otherwise stated. Statistical significance for the primary efficacy endpoint will be based on a two-tailed test of the null hypothesis at the alpha=0.05 level of significance.
	Efficacy analyses will be performed primarily for the intent-to-treat (ITT) population. Efficacy analyses using the per-protocol (PP) population will be in support of the ITT analyses.
	The Safety population will include all subjects enrolled in the study who were dispensed and applied test article at least once. Subjects will apply their first application of the test article in the clinic during their Baseline Visit on Day 1. Subjects enrolled in the study who were randomized and dispensed test article will be considered the ITT population. Subjects will be included in the PP efficacy analyses if they have completed the study without significant protocol deviations. Subjects who discontinue from the study prematurely due to treatment failure, as determined by the investigator, will also be included in the PP population as treatment failures.
	Demographic and baseline characteristics will be summarized by treatment group for the ITT, PP, and Safety populations. Frequency counts and percentages will be reported for categorical data and the number of subjects with non-missing data (n), mean, median, standard deviation (SD), minimum and maximum will be reported for the continuous variables.

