	Efficacy Analyses: Efficacy will be demonstrated if the proportion of HBP Foam treated- subjects with IGA "treatment success" at Day 15 is statistically significantly greater than the proportion of VEH Foam-treated subjects that are "treatment successes" at Day 15 based on a two-sided test at the alpha=0.05 level of significance. The treatment groups will be compared with respect to IGA treatment success at Day 15 using the Cochran-Mantel-Haenszel (CMH) test stratified by center.
	Subjects without data at Day 15 will be considered to be treatment failures (i.e., to not have achieved the primary endpoint). Note: this definition includes subjects who drop out of the study prior to Day 15 for any reason.

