### 5.1.1 Inclusion Criteria

- 1. Subject is male or non-pregnant female and is at least 18 years of age at the time of the Screening Visit.
- 2. Subject has provided written informed consent.
- 3. Subject is willing and able to apply the test article(s) as directed, comply with study instructions and commit to all follow-up visits for the duration of the study.
- 4. Subject has a clinical diagnosis of stable plaque psoriasis involving body surface area (BSA) (excluding the face, scalp, groin, axillae and other intertriginous areas).
- 5. Subject has an Investigator's Global Assessment (IGA) score of at least three (3 = moderate) at the Baseline Visit.
- 6. Females must be post-menopausal, surgically sterile or use an effective method of birth control with a negative urine pregnancy test (UPT) at the Baseline Visit.

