### 7. RANDOMIZATION ASSIGNMENT

[figure not shown]
Subjects who are eligible for enrollment into the study will be randomized to receive HBP Foam or VEH Foam in a 1:1 ratio. The randomization scheme will be blocked by investigational site. At each site, subject kits (each containing three units) will be dispensed in ascending order as subjects are enrolled. At each site, the study staff will add the site number (provided to each site) and the subject number (starting with 001) to each kit label. The kit number dispensed to each subject will also be recorded on the source documents and CRFs. Treatment group designation will remain blinded until the final database is locked (unless unblinding is required as described in Section 15). Subject enrollment at the sites will be competitive. All subjects will apply the topical formulations as directed by the investigator.

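### The primary test is valid but leaves out Baseline IGA (3 vs 4), which sets how far a subject must improve; adding it as one covariate would guard against chance imbalance at almost no cost in power.

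*Combined protocol and SAP*

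**What the plan says.** - **Entry (5.1.1).** "Subject has an Investigator's Global Assessment (IGA) score of at least three (3 = moderate) at the Baseline Visit". The scale runs from 0 to 4, so each eligible subject scores 3 or 4.
- **Endpoint (17.2.1).** Success is an IGA of 0 or 1 "with at least a two grade decrease in severity score relative to Baseline".
- **Randomization (7).** "The randomization scheme will be blocked by investigational site". No stratification by Baseline IGA is stated.
- **Primary test (17.3.1.1).** The arms are compared "with respect to IGA treatment success rates at Day 15 using the CMH test stratified by center". The synopsis agrees: "using the Cochran-Mantel-Haenszel (CMH) test stratified by center".
- **Sample size (synopsis and 17.1).** "A sample size of 200 subjects for each treatment group", for success rates of "20% for HBP Foam versus 9% for VEH Foam", with power 0.85 by Fisher's exact test at two-sided 0.05.
- **Other uses of Baseline IGA.** It is only tabulated by arm (17.3.1.3). It is not a subgroup factor (17.8). In 17.5 the one severity covariate is plaque elevation, in the multiple-imputation model. By contrast, the pruritus analysis is adjusted for its own Baseline score (17.3.1.3).

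**The concern.** The endpoint sets a different distance for the two kinds of subject: at least two grades from IGA 3, at least three from IGA 4. A baseline value that sets this distance is a natural candidate for a strong predictor of success. It is scored for everyone before the first application, so using it needs no new data.

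Blocking by site does not balance Baseline IGA between arms. If more IGA 4 subjects fall on one arm by chance, a center-only test carries that difference into the primary p-value. An excess on vehicle flatters HBP Foam; an excess on HBP Foam costs power. If the imbalance is noticed only after unblinding, any adjustment made then is post hoc, which is the reason to settle the matter in advance.

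**Working it through.** **Inputs from the documents.** 200 per arm; success rates 20% and 9%; two-sided alpha 0.05; about 20 centers, so about 10 subjects per arm per center.

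**Inputs assumed, because the documents do not give them.** Share of IGA 4 subjects, q: 10%, 20%, 30%. Odds ratio (OR) for success, IGA 4 vs 3: mainly 0.15 to 0.5, with 1 as the case of no prognostic value. The same OR is used in both arms.

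**Step 1: the plan's own figure.** Exact enumeration of the two-sided Fisher test at 200 per arm, 20% vs 9%, gives power 0.858. The stated 0.85 is reproduced.

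**Step 2: the planned test.** In simulation, the center-stratified CMH has power 0.885-0.899 and two-sided size 0.047-0.051. It is valid and exceeds its target.

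**Step 3: change in power with Baseline IGA.** Two sets of simulations were run, one with equal and one with unequal center sizes. Changes are in percentage points against the center-only test.

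| OR, IGA 4 vs 3 | IGA as one main effect beside center | CMH by center x IGA (about 40 strata) |
|---|---|---|
| 1 | -0.3 to 0 | -1.8 to -1.4 |
| 0.5 | -0.1 to +0.3 | -1.1 to -0.7 |
| 0.25 | +0.3 to +0.9 | -0.3 to -0.1 |
| 0.15-0.4 (unequal centers) | +0.1 to +1.3 | -0.8 to +0.4 |

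Over OR 0.15-0.5 the main-effect form changes power by about 0 to +1.3 points; its two-sided size was 0.044-0.054 in the unequal-center runs. Crossing the strata makes them sparse and mostly loses power.

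**Step 4: how large an imbalance chance produces.** SD of the between-arm difference in IGA 4 share = sqrt(2q(1-q)/200):

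- q = 10%: sqrt(2 x 0.1 x 0.9/200) = 3.0 points, so 8 points is 8/3.0 = 2.7 SD.
- q = 20%: 4.0 points, so 8 points is 2.0 SD.
- q = 30%: 4.58 points, so 8 points is 1.75 SD.

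The simulated 95th percentile of the absolute difference is 6 to 9 points.

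**Step 5: effect of 8 points more IGA 4 on vehicle, with no treatment effect.** Take a common success rate of (20% + 9%)/2 = 14.5%. Let p3 and p4 be the success rates at IGA 3 and 4. They solve (1-q)p3 + q p4 = 0.145 and [p4/(1-p4)]/[p3/(1-p3)] = OR.

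- Shift = (p3 - p4) x 0.08.
- SE = sqrt(2 x 0.145 x 0.855/200) = 0.0352, used throughout as an approximation.
- Conditional one-sided error = 1 - Phi(1.96 - shift/SE).

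| q | OR | p3 | p4 | Shift (points) | Shift/SE | Error |
|---|---|---|---|---|---|---|
| 10% | 0.4 | 0.154 | 0.068 | 0.69 | 0.195 | 0.039 |
| 10% | 0.15 | 0.158 | 0.027 | 1.05 | 0.297 | 0.048 |
| 20% | 0.4 | 0.163 | 0.072 | 0.73 | 0.206 | 0.040 |
| 20% | 0.15 | 0.174 | 0.031 | 1.14 | 0.325 | 0.051 |
| 30% | 0.4 | 0.174 | 0.078 | 0.77 | 0.219 | 0.041 |
| 30% | 0.15 | 0.192 | 0.035 | 1.26 | 0.359 | 0.055 |

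The shift is 0.7-1.3 points and the error 0.039-0.055, against a nominal 0.025. With the imbalance reversed, 1 - Phi(1.96 + shift/SE) gives 0.010-0.016.

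**Step 6: effect on power when the excess falls on HBP Foam.** In the roughly 5% of simulated trials with most excess IGA 4 on HBP Foam, at OR 0.25-0.5, power was 0.82-0.89 with center only and 0.88-0.91 with IGA as a main effect. Each figure rests on about 500 of 10,000 trials, so its standard error is about sqrt(0.85 x 0.15/500) = 0.016.

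**The case against.** The strongest reply is that nothing here is an error. The analysis follows the design: blocking by site, test stratified by center. Size is nominal and the stated power is met. An imbalance would be visible in the planned baseline tables. The conditional-error argument looks at a tail event in one direction; the opposite imbalance is equally likely and lowers the error, and the same argument could be made for any prognostic variable left out. All of this stands. A reader might infer that the primary test has an inflated false-positive rate; steps 2 and 5 do not support that.

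A reader might also infer that success depends on Baseline IGA by construction. The definition fixes the distance to be covered, not the chance of covering it, and the documents report no success rates by Baseline IGA. Nor is adjustment a free gain: at OR 1 it costs up to about 0.3 points of power, and at OR 0.5 the gain is hardly distinguishable from zero.

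The edit also reaches beyond one sentence, because 17.5 is worded as repeats of the primary analysis, and the key secondary endpoints in 17.3.1.2 use the center-stratified CMH.

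These points limit the claim but do not remove it. Seeing an imbalance in a baseline table is not the same as having a prespecified analysis that accounts for it, and Baseline IGA has a better claim than most covariates because the endpoint is measured against it.

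**Conclusion.** This is an optional improvement, not a flaw. The center-only CMH can stand as a valid primary test. Leaving out Baseline IGA forgoes about 0 to 1.3 points of power and, more usefully, protection when IGA 4 subjects fall unevenly. With an 8-point excess on vehicle and no treatment effect, the conditional one-sided error is 0.039-0.055 instead of 0.025; averaged over all randomizations it stays nominal.

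The figures rest on assumed values for the IGA 4 share (10-30%) and the odds ratio (0.15-0.5 for power, 0.15-0.4 for the conditional error), on one odds ratio for both arms, and on no missing data in the equal-center simulations. If Baseline IGA turns out to be weakly prognostic, little is gained and little is lost.

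**What to change.** Before unblinding:

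1. In 17.3.1.1 and the synopsis, keep center as the stratification factor and add Baseline IGA (3 vs 4) as one covariate. One suitable form is logistic regression conditional on center, with treatment and Baseline IGA in the model and a score test for treatment.
2. Name the center-only CMH as the supportive analysis.
3. Align 17.5, so that it is clear which test each repeat of the primary analysis uses.
4. Leave the key secondary tests in 17.3.1.2 as they are.

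Crossing center with Baseline IGA in the CMH is not a substitute, because the sparse strata usually lose power.

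If the sponsor prefers the CMH as primary, the minimum is to prespecify the Baseline-IGA-adjusted model in 17.5 as a sensitivity analysis.

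The cost is some wording, a few lines of code, a less familiar primary test, and a negligible loss of power if Baseline IGA is not prognostic. No extra subjects or data are needed.

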#### 17.3.1.2 Key Secondary Efficacy Analyses

If the primary analysis is statistically significant (p<0.05), then a "gatekeeping" approach will be used to test the three key secondary endpoints:

- The proportion of subjects rated a "treatment success" for plaque elevation at Day 15.
- The proportion of subjects rated a "treatment success" for scaling at Day 15.
- The proportion of subjects rated a "treatment success" for erythema at Day 15.

Thus, if the analysis of the first key secondary endpoint is statistically significant at the alpha=0.05 level of significance, then the second key secondary endpoint will be tested at the alpha=0.05 level of significance. If this analysis is statistically significant, then the third key secondary endpoint will be tested at the alpha=0.05 level of significance. However, if any previous analysis (including the primary analysis) is not statistically significant, all subsequent comparisons will be exploratory rather than confirmatory.

The treatment groups will be compared with respect to the proportions of subjects with "treatment success" for each of the signs of psoriasis at Day 15 using the CMH test stratified by center. Subjects with Baseline scores of 0 or 1 will be excluded unless the corresponding sign score at Day 15 is >1.

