### Clinical Signs of Psoriasis

The frequency distributions of the secondary efficacy endpoints, clinical signs of psoriasis (scaling, erythema, and plaque elevation), will be summarized by treatment group at Baseline, and at Days 8 and 15. The treatment groups will also be compared with respect to "treatment success" rates at Day 8 for each sign of psoriasis using the CMH test stratified by center. Subjects with Baseline scores of 0 or 1 will be excluded unless the corresponding sign score at Day 8 is >1.

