#### 17.4 Imputation of Missing Data

The primary efficacy endpoint is defined as a success rate. Any subject who cannot be confirmed as a "success" is a treatment failure; therefore, missing data is imputed as treatment failure.

The key secondary efficacy endpoints will be the proportion of subjects rated a "treatment success" for each of the clinical signs of psoriasis (scaling, erythema and plaque elevation) at Day 15. Subjects without data at Day 15 will be considered treatment failures, i.e., to not have achieved "treatment success". Note that this definition includes subjects who drop out of the study prior to Day 15 for any reason.

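### The key secondary sign analyses include or drop subjects with Baseline scores of 0 or 1 according to their Day 15 result

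*Combined protocol and SAP*

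**What the plan says.** - Section 17.2.1 counts a sign as a success when the score is 0 or 1 "with at least a two grade decrease in severity score relative to Baseline". Plaque elevation, scaling and erythema at Day 15 are the key secondary endpoints. They are tested in that fixed order after the primary, each at 0.05, by a CMH test stratified by center.
- Section 17.3.1.2 defines who enters those tests: "Subjects with Baseline scores of 0 or 1 will be excluded unless the corresponding sign score at Day 15 is >1".
- The Day 8 sign comparisons carry the same rule, in the synopsis and in section 17.3.1.3: "Subjects with Baseline scores of 0 or 1 will be excluded unless the corresponding sign score at Day 8 is >1".
- Section 17.3 sets the main population: "Efficacy analyses will be performed primarily for the intent-to-treat (ITT) population".
- Section 17.4 says of the signs: "Subjects without data at Day 15 will be considered treatment failures". It adds: "Note that this definition includes subjects who drop out of the study prior to Day 15 for any reason". It makes no exception for a low Baseline score.
- Section 5.1.1 requires: "Subject has an Investigator's Global Assessment (IGA) score of at least three (3 = moderate) at the Baseline Visit". No inclusion criterion sets a minimum for an individual sign, and section 10.1 says the IGA is not computed from the sign scores. A subject can therefore enter with a sign at 0 or 1.

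**The concern.** An analysis set should be settled by what is known at randomization. Here, part of it is settled by the outcome. Among subjects who start a sign at 0 or 1, those who end at 0 or 1 are dropped, including any who go from 0 to 1. Those who end above 1 are kept and can only be failures. The rule therefore lowers the success rate in whichever arm has more such subjects. If HBP Foam works, that is plausibly the VEH arm, which would enlarge the apparent difference.

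These are the only confirmatory secondary tests in the plan. In addition, two programmers working from sections 17.3.1.2 and 17.4 could build different denominators. The sensitivity analyses in section 17.5 cover only the primary endpoint, so nothing elsewhere in the plan would reveal the effect.

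**Working it through.** **The plan's own figure.** The synopsis gives 200 per arm, 20% versus 9%, Fisher's exact test, two-sided 0.05, power 0.85. Exact enumeration gives power 0.858, so the figure reproduces. It concerns the primary endpoint; no figure is given for the signs.

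**Step 1: what the clause does.** A two-grade fall from 0 or 1 is impossible. By Baseline and Day 15 score:

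| Baseline sign score | Day 15 score | Section 17.3.1.2 | Section 17.4 |
|---|---|---|---|
| 2 or more | observed | analyzed | not addressed (not missing) |
| 2 or more | missing | analyzed | failure |
| 0 or 1 | 0 or 1 | excluded | not addressed (not missing) |
| 0 or 1 | above 1 | analyzed, always a failure | not addressed (not missing) |
| 0 or 1 | missing | excluded, as a missing score is not >1 | failure |

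The third and fourth rows show the dependence on outcome. The last row is where the two sections disagree.

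**Step 2: effect on the rate.** Let f be the share of subjects with a Baseline score of 0 or 1, p the true success rate among the rest, and w the proportion of low-baseline subjects reaching >1. The expected rate under the written rule is

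(1 - f)p / [(1 - f) + f*w].

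Neither f nor w is in the documents; all values below are assumptions. With f = 0.05 and p = 0.20 in both arms:

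- w = 0.1: 0.19 / 0.955 = 19.90%
- w = 0.3: 0.19 / 0.965 = 19.69%
- w = 0.6: 0.19 / 0.980 = 19.39%

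In counts, 200 x 0.05 = 10 low-baseline subjects per arm. Of these, 1 is readmitted at w = 0.1, 3 at w = 0.3 and 6 at w = 0.6.

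**Step 3: effect on the test.** Simulated CMH test, 20 centers with 10 per arm each, 100,000 trials per scenario, two-sided 0.05, p = 20% or 35% in both arms. Each range covers both values of p and, where several shares are listed, all of them. The gate is not modelled. The HBP tail is the share of trials significant in favor of HBP Foam (nominal 2.5%).

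| Reaching >1, HBP / VEH | f | HBP tail | Two-sided error |
|---|---|---|---|
| 30% / 30% | 2%, 5%, 10% | 2.5-2.6% | 5.0-5.2% |
| 10% / 30% | 2% | 2.6-2.7% | 4.9-5.3% over the three shares |
| 10% / 30% | 5% | 2.8-2.9% | as above |
| 10% / 30% | 10% | 3.2-3.6% | as above |
| 10% / 60% | 2% | 2.8-3.0% | 5.0-5.1% |
| 10% / 60% | 5% | 3.4-3.8% | 5.3-5.4% |
| 10% / 60% | 10% | 4.5-5.5% | 5.9-6.5% |
| 30% / 10% | 2%, 5%, 10% | 1.7-2.4% (VEH tail 2.7-3.5%) | not tabulated |
| Baseline-only set | 2%, 5%, 10% | 2.4-2.5% | 4.9-5.0% |

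Two-sided error moves less than the HBP tail because the VEH tail shrinks. At f = 10%, p = 35% and 10% / 30%, the tails are 3.56% and 1.78%, total 5.34%. The tilt grows with the success rate: a separate run of 40,000 trials at f = 10% and 5% / 30% gave an HBP tail of 3.3% at p = 20% and 4.4% at p = 50%.

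**Step 4: power.** Borrowing the primary planning rates (20% versus 9%) for a sign, with f = 5%: 87.2% for the Baseline-only set, and under the written rule 87.9% (10% / 30%) or 89.2% (10% / 60%). The difference is produced by the readmitted failures.

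**The case against.** The strongest reply is that an inert product gains nothing. If treatment affects no sign outcome, readmission is equal and the type I error is kept. A gap in the proportion reaching >1 would itself be a drug effect, and the rule also counts worsening on HBP Foam against HBP Foam. That is correct, and it limits the charge. But the endpoint is clearance, and worsening among subjects who cannot clear should not enter it through the denominator.

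Second, the numbers are probably small. Entry needs an IGA of at least 3 and stable disease, so signs at 0 or 1 should be uncommon, and 60% reaching >1 in two weeks on VEH Foam is a deliberately extreme case. This stands. At a share of 5% or less with the milder gap, the HBP tail stays below 3%.

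Third, section 17.3.1.2 can be read as saying who is analyzed and section 17.4 as saying how missing values are scored within that set. That reading is reasonable, but section 17.4 does not state it. The gap is narrow: with an assumed 5% share and 10% missing, 200 x 0.05 x 0.10 = 1 subject per arm.

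Fourth, a Baseline-only set is not the only sound repair. Keeping every low-baseline subject as a failure is equally independent of outcome, stays closer to ITT, and has nearly the same power (about 87% at 20% versus 9% and a 5% share). This is also correct, and the choice belongs to the sponsor.

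**Conclusion.** The concern holds. Under the written rule, membership of the analysis set for the three gatekept sign endpoints depends on the Day 15 score under test, and every readmitted subject is a failure by definition. This follows from the text and needs no assumption. The direction and size of any bias do rest on assumptions: the low-baseline share and the proportions reaching >1 in each arm. Over the range tried, the effect runs from none (equal proportions) through a slight tilt at shares up to 5% to an HBP tail of about twice nominal in the extreme 10% share case. The disagreement with section 17.4 is real but confined to subjects who have both a low Baseline score and no Day 15 score. The primary IGA analysis is untouched, because every eligible subject starts at 3 or above. The Day 8 comparisons are supportive only and add little weight. This should be fixed, but it does not threaten the trial's main conclusion.

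**What to change.** Define the set by Baseline alone. Suggested wording for section 17.3.1.2: *Each sign is analyzed in ITT subjects whose Baseline score for that sign is 2 or more, whatever the later score; within that set, a missing Day 15 score counts as failure.*

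- Delete the exception at Day 15 in section 17.3.1.2, and at Day 8 in the synopsis and section 17.3.1.3.
- State in section 17.4 that failure imputation for the signs applies within this set.
- Report the number of subjects with a Baseline score of 0 or 1, by sign and arm.

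If the sponsor prefers to keep all ITT subjects, counting every low-baseline subject as a failure also removes the problem and agrees with section 17.4 as written.

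The cost is wording, provided the change is made before unblinding. The analyzed number falls only by the few low-baseline subjects who would have reached >1. The simulated power given up at a 5% share (0.7 to 2.0 points, from 87.9-89.2% to 87.2%) is the part that came from readmitting certain failures.
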